### 7.5.2 Clinical Laboratory Evaluation

Clinical laboratory assessments will be done at every scheduled visit, as well as at any unscheduled visits. Assessments of serum hormonal levels will be done at the

Randomization, 12 Month Visits, 24 month and at any unscheduled study visits. Summary tables will be presented for all scheduled visits. Unscheduled visits will be displayed in listings only. Values outside the normal range will be flagged.

Laboratory data in this study consist of hematology (WBC count, WBC differential, RBC count, RDW, HCT, HgB, MCV, MCH, MCHC, Platelet count, MPV), serum chemistry (Glucose, Calcium, Total protein, Albumin, Sodium, Potassium, CO2, Chloride, BUN, Creatinine, ALP, ALT, AST, Bilirubin), PSA levels and hormonal levels (Testosterone, DHT, Dihydroepiandrosterone, Androstenedione, Estradiol).

The results will be summarized by treatment group for actual values and change from baseline. Normal ranges will be applied to identify values that are outside the normal ranges. Shift analysis tables will be provided for each parameter to present shift from baseline to each visit for low, normal and high values.

Laboratory results will be graded using the Version 5.0 of the NCI-CTCAE criteria, updating to the latest version per sponsor decision. Shift tables will be produced and will report the baseline NCI-CTCAE grade vs. the worst grade recorded at any post-baseline visit.

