**Table 2 Schedule of Assessments**

Study Visit Name	Screening	Randomization	3m	6m	9m	12m	15m	18m	21m	24m	>24m, q6m 	Unscheduled 
Study Day	-28 to -7	1	85	176	267	358	455	545	635	730	>730	n/a
Week	-4 to -1	1	13	26	39	52	65	78	91	104	>104	n/a
Window (days)			± 7	± 7	± 7	± 7	+7	+7	+7	+7	± 7	n/a
Informed Consent	X											
Medical History 	X		X 									
Inclusion/Exclusion Criteria	X		X									
Randomization		X										
Vital Signs	X		X	X	X	X	X	X	X	X	X	X
Physical Examination, Weight 	X			X	X	X	X	X	X	X	X	X
12-Lead ECG	X 											
MUGA/Echocardiogram 	X 											
Clinical Labs 	X		X	X	X	X	X	X	X	X	X	X
Serum hormone levels 		X			X				X			X
Serum PSA 	X		X	X	X	X	X	X	X	X	X	X 
Digital Rectal Examination	X			X		X		X		X		X 
Transrectal ultrasound-guided prostate biopsy(12 core) 	X 				X				X			X 
BFI 		X	X	X		X		X		X		
SF-12 		X		X	X		X		X		X	
EPIC 		X		X	X		X		X		X	
MAX-PC 		X		X	X		X		X		X	
Adverse Events 	X		X	X	X	X	X	X	X	X	X	X
Concomitant Medications	X		X	X	X	X	X	X	X	X	X	X
Therapies and Outcomes Review	X		X	X	X	X	X	X	X	X	X	X
Study Drug Dispensing 	X		X	X	X	X						
Blood Sample for Potential Future Analysis(optional) 	X		X	X	X	X	X	X	X	X	X	X

1. Subjects will be followed every 6 months until the last subject (study-wide) has completed the 24m Visit.
2. Unscheduled visits may be performed at any time during the study whenever necessary to assess for or follow-up on adverse events (AEs), at the subject's request or if deemed necessary by the investigator.
3. Medical history will include capturing information about any first degree relatives with prostate cancer. Any updates to the subject's medical history will be recorded at the Randomization Visit (Study Day 1) prior to randomization.
4. A complete physical examination will be completed at the Screening Visit. For all visits after the Randomization visit, only a brief physical examination is required.
5. This procedure (if required) must be done within 28 days prior to randomization.
6. A multi-gated acquisition (MUGA) scan or echocardiogram is only required if the subject has a history of anthracycline or anthracenedione (mitoxantrone) treatment.

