#### **7.5.2.1 Liver Enzymes and Total Bilirubin**

Detailed testing for liver enzymes, specifically ALT, AST, and Total Bilirubin, are done at every study visit starting with Randomization and up to month 24 and unscheduled.

Confirmed abnormalities will be characterized as moderate and severe where ULN:

Moderate: AST or ALT [ $>3 \times$  ULN (in patients without liver metastases);  $>5 \times$  ULN (in patients with liver metastases)] or (Total Bilirubin  $>2 \times$  ULN).

Severe: AST or ALT  $>3 \times$  ULN and Total Bilirubin  $>2 \times$  ULN.

In addition, the subject will be considered to have severe hepatic abnormalities for any of the following:

- ALT or AST  $> 8 \times$  ULN.
- ALT or AST  $> 5 \times$  ULN for more than 2 weeks (in the absence of liver metastases).
- ALT or AST  $> 3 \times$  ULN and INR  $> 1.5$  (If INR testing is applicable/evaluated).
- ALT or AST  $> 3 \times$  ULN with the appearance of fatigue, nausea, vomiting, right upper quadrant pain or tenderness, fever, rash and/or eosinophilia ( $>5\%$ ).

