### **7.10.3 Visit Windows**

For reporting by nominal time point, assessments will be imputed with the following windowing conventions:

Nominal Visit	Target Study Day (per Section V of the Protocol)	Study Day Window (inclusive)
3 Month	85	43 to 130
6 Month	176	131 to 221
9 Month	267	222 to 312
12 Month	358	322 to 406
15 Month	455	407 to 500
18 Month	545	501 to 590
21 Month	635	591 to 682
24 Month	730	683 to 754

For nominal time points with a nominal visit corresponding, this value will be used. If no nominal assessment exists, but an unscheduled assessment is windowed into the time point, this windowed assessment will be used. If more than one unscheduled assessment exists in the window (and there is no nominal visit assessment), the latest value will be used.

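### Section 7.5.2 confines unscheduled laboratory results to listings without exempting the worst-grade shift tables or the liver categories; separately, the visit windows leave days 313–321 unassigned

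*SAP*

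**What the plan says.** Section 7.5.2 of the SAP first sets out collection: "Clinical laboratory assessments will be done at every scheduled visit, as well as at any unscheduled visits". It then gives two reporting rules in succession: "Summary tables will be presented for all scheduled visits", followed by "Unscheduled visits will be displayed in listings only". Neither carries an exception. Later in the same section, the CTCAE shift tables are defined as "the baseline NCI-CTCAE grade vs. the worst grade recorded at any post-baseline visit".

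Section 7.5.2.1 says that ALT, AST and total bilirubin tests "are done at every study visit starting with Randomization and up to month 24 and unscheduled". It continues: "Confirmed abnormalities will be characterized as moderate and severe". One of its criteria for a severe abnormality is an ALT or AST elevation lasting more than two weeks.

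Section 7.10.3 sets the visit windows. A value from the nominal visit is used where there is one. Otherwise: "If no nominal assessment exists, but an unscheduled assessment is windowed into the time point, this windowed assessment will be used". If several unscheduled values qualify, the latest is taken. The 9 Month window is days 222 to 312 and the 12 Month window is days 322 to 406.

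Table 2, footnote 2, gives the assessment and follow-up of adverse events as one purpose of unscheduled visits, alongside subject request and investigator judgement.

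**The concern.** An unscheduled visit after baseline is a post-baseline visit, and 7.5.2 says that laboratory samples are taken there. A shift table of the worst post-baseline grade should therefore draw on those samples, yet the listings-only sentence, as written, keeps them out of every table. The liver categories raise the same question. Confirming an abnormality, or showing that it lasted more than two weeks, normally needs a repeat sample soon after the first, and the scheduled visits do not provide one.

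The SAP does not say which rule prevails, so two programmers could produce different worst-grade tables and liver classifications from the same data and both could cite the SAP. The output at stake is the laboratory safety reporting, not the primary analysis.

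The window table raises a separate and smaller matter. Nine consecutive study days belong to no visit, so an unscheduled assessment on one of them cannot stand in for a missing nominal value.

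**Working it through.** The SAP states no figure on this point to reproduce. The check compares the rules and then asks what scheduled visits alone can show.

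**1. The rules side by side**

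| Output | Source | Needs unscheduled values? | Under a literal listings-only rule |
|---|---|---|---|
| By-visit summaries | 7.5.2 | No, except values windowed under 7.10.3 | Little or no effect |
| Worst-grade shift table | 7.5.2 | Yes, by its own definition | Unscheduled values dropped |
| Liver categories | 7.5.2.1 | Yes: unscheduled tests are named; confirmation and duration are required | Unscheduled values dropped if the categories are tabulated |

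**2. Spacing of scheduled laboratory visits**

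Target days (Table 2 and 7.10.3): 1, 85, 176, 267, 358, 455, 545, 635, 730. Day 1 is the Randomization visit.

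Differences: 84, 91, 91, 91, 97, 90, 90, 95. Mean = 729 / 8 = 91.1 days.

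The month 3 to month 12 visits have windows of ±7 days. With one visit as late as allowed and the next as early as allowed, the shortest interval is 91 − 7 − 7 = 77 days.

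**3. What this means for the two-week liver criterion**

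On scheduled samples alone, persistence can be supported only by two elevated values at least 77 days apart, or 91 days on target. Against 14 days, that is 77 / 14 = 5.5 to 91 / 14 = 6.5 times the stated duration. An elevation lasting three or four weeks could not be documented as persistent.

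**4. Chance that a scheduled visit falls inside a short episode**

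Assumption, not in the SAP: an episode of L days starts at a random point in a visit interval of I days, with L ≤ I. Then P = L / I. The episode lengths are illustrative.

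| L (days) | I = 91 | I = 97 to I = 84 |
|---|---|---|
| 15 | 15 / 91 = 0.165 | 0.155 to 0.179 |
| 28 | 28 / 91 = 0.308 | 0.289 to 0.333 |
| 42 | 42 / 91 = 0.462 | 0.433 to 0.500 |

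For episodes of two to four weeks, roughly 70% to 85% would contain no scheduled sample. Such an episode is seen in the laboratory data only if an unscheduled sample is drawn. These are chances per episode, not estimates of how many subjects are affected.

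**5. The window table**

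| Adjacent visits | Midpoint of targets | First window ends | Next window starts |
|---|---|---|---|
| 3 / 6 Month | 130.5 | 130 | 131 |
| 6 / 9 Month | 221.5 | 221 | 222 |
| 9 / 12 Month | 312.5 | 312 | **322** |
| 12 / 15 Month | 406.5 | 406 | 407 |
| 15 / 18 Month | 500 | 500 | 501 |
| 18 / 21 Month | 590 | 590 | 591 |
| 21 / 24 Month | 682.5 | 682 | 683 |

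Six of the seven pairs are contiguous and split at the midpoint. The 9 / 12 Month pair is not: 322 − 312 − 1 = 9 days (313 to 321) are unassigned. The pattern of the other rows gives a start of day 313.

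**The case against.** The strongest reply is that a consistent reading exists. The listings-only sentence directly follows the one on summaries for scheduled visits, so the pair can be taken to mean only that an unscheduled visit gets no row of its own in a by-visit table. The worst-grade shift table is not a by-visit table and has its own, more specific rule. The liver classification is made per subject, and 7.5.2.1 names unscheduled tests expressly. This is a sensible reading and may be the intended one. A reader might infer that the rules flatly contradict each other; the text does not go that far. It does leave the choice of reading open, and that part of the concern stands.

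Other points on this side also hold:

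- Section 7.10.3 does not clearly conflict with 7.5.2. An unscheduled value that fills an empty nominal time point is reported under a scheduled visit. Because the latest value is taken, not the worst, windowing would not recover a peak in any case.
- Section 7.5.2.1 says that abnormalities will be characterised but names no table, so the effect on liver output depends on how the categories are presented.
- There is partial mitigation. Section 7.5.1 tabulates adverse events by maximum CTCAE grade, serious events, and events leading to discontinuation of study drug. Peaks reported as adverse events reach those tables, and unscheduled laboratory results remain in the listings.
- A reader might infer a larger loss in the enzalutamide arm, on the expectation of more visits prompted by adverse events. The SAP gives no rate of unscheduled visits by arm, so this is unsupported.
- The nine-day gap has no bearing on worst grade or the liver categories, since neither is defined by window. A nominal-visit value is used whatever its day, and the 12 Month visit is planned for days 351 to 365. Only a subject with an unscheduled assessment on days 313 to 321 and no nominal value to report is affected.

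**Conclusion.** The concern holds as an ambiguity with a real consequence if the sentence is applied literally. In that case the worst-grade shift tables and the 7.5.2.1 categories can omit peak or confirmatory values, which scheduled visits about 91 days apart (at least 77 from month 3 to month 12) often cannot supply. It cannot be said that values will be omitted, because the narrower reading is open to the programmer. The number of subjects affected and any difference between arms cannot be determined from the SAP. The chances per episode rest on the random-start assumption and on illustrative episode lengths.

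The omission of days 313 to 321 from 7.10.3 is a plain error that does not depend on any reading. Its effect is small and limited to reporting by nominal time point.

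**What to change.** 1. In 7.5.2, limit the listings-only rule to by-visit summary tables, and exempt unscheduled values assigned to a nominal visit under 7.10.3.
2. In 7.5.2 and 7.5.2.1, state that worst post-baseline grade and all liver categories use every post-baseline result, scheduled or unscheduled.
3. In 7.10.3, start the 12 Month window at day 313.

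The cost is two sentences, one number and a check of the programming filter. No new data are needed, and no clinical threshold or visit schedule changes. Reported worst grades may be somewhat less favourable than under the literal rule.

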**CCI**

#### **3.2 Study Design**

This is a multicenter, randomized, open label exploratory study, conducted in the US and Canada, evaluating the efficacy and safety of enzalutamide for extension of time to prostate cancer progression (pathological or therapeutic) in subjects with clinically localized, histologically proven prostate cancer that is categorized as low risk or intermediate risk and who are under AS. A total of 222 subjects from approximately 50 centers will be enrolled. Subjects are eligible if they were diagnosed within 6 months of screening and have been on AS. A minimum of ten cores from transrectal ultrasound-guided prostate biopsy (mpMRI targeted versus non-mpMRI targeted) are required; confirmatory biopsy before entering the study is not required and is done at the discretion of the investigator.

Low risk is defined as T1c-T2a, PSA $<$ 10, N0, M0 (or presumed N0, M0 if computerized tomography [CT]/bone scan not done due to low risk of metastases), GS  $\leq$  6, ECOG status  $\leq$  2 and estimated life expectancy  $>$  5 years. Intermediate risk is defined as T2b-T2c, PSA $<$ 20, N0, M0 (or presumed N0, M0 if CT/bone scan not done), GS  $\leq$  7 (3+4 pattern only), ECOG status  $\leq$  2 and estimated life expectancy  $>$  5 years.

Prostate cancer progression is defined as either therapeutic progression or pathological progression. Therapeutic progression is defined as the earliest occurrence of primary therapy for prostate cancer (prostatectomy / radiation / focal therapy / systemic therapy). Pathological progression is defined as increase in primary or secondary Gleason pattern by  $>$  1 or higher

proportion of cancer positive cores (>15% increase). Subjects will be stratified by low versus intermediate risk and type of biopsy performed (mpMRI targeted versus non-mpMRI targeted).

Subjects will be randomized (1:1) either to receive treatment with enzalutamide (160 mg), administered as four 40 mg capsules, by mouth, once daily or to AS during the one year study treatment period. Following the one year treatment period, all subjects will be followed for one additional year. Subjects will be followed up every 3 months for these 2 years, after which follow-up will either be every 6 months or unscheduled until the last subject finished their 2 year follow-up. Serum PSA will be measured at baseline and every 3 months during subsequent follow-up visits.

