## 4 SAMPLE SIZE

This study is designed to evaluate time to prostate cancer progression (pathological or therapeutic progression) as the primary endpoint. The overall two-sided type I error for this study is set at 0.05 level. The characteristics of time to prostate cancer progression (pathological or therapeutic progression) are used to determine the total sample size and overall duration.

A sample size of 222 subjects randomized in a 1 to 1 manner accrued over one year, a study duration of 3 years, loss-to follow-up of 16%, an assumed underlying hazard ratio of 0.52 and a three year median time-to-progression for the Control group (0.2310 rate) will result in 72 events (Fleshner et al., 2012). This sample size is sufficient to power this study at 80% with a two-sided type I error rate of 5%.

The assumed hazard ratio of 0.52 is consistent with Fleshner et al. (2012). Specifically, the Fleshner study is powered to detect a 39% failure rate reduction in the treated group with respect to a three year 45% failure rate in the control group. We used a more conservative 30% failure rate reduction for the treated group and a 50% three year failure rate for the control group. This resulted in parameter estimates of 0.2310 for the Control group and 0.1189 for the Treatment group, and thus, resulted in the hazard rate of 0.52.

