## 6.4 Other Variables

To clearly state, the following variables are defined:

- Month = 30.4375 days. Year = 365.25 days.
- $BMI(kg/m^2) = Weight(kg) / Height(m^2)$
- Age at randomization=  $\text{floor}((\text{intck}(\text{'month'}, \text{birth date}, \text{randomization date}) - (\text{day}(\text{randomization date}) < \text{day}(\text{birth date}))) / 12)$
- Time since initial/histological diagnosis (years) =  $[(\text{date informed consent signed} - \text{date of initial/histological diagnosis}) + 1] / 365.25$ .
- Time since initial diagnosis to Randomization (years) =  $[(\text{date of Randomization} - \text{date of initial diagnosis}) + 1] / 365.25$ .
- The duration of treatment was calculated as the (last dose date – first dose date) + 1.
- Number of pills taken from one visit to the next = number of pills dispensed – number of pills returned.
- Study drug compliance at each visit is calculated as =  $[(\text{number of pills dispensed} - \text{number of pills returned}) / (4 * \text{number of days in the visit period})] * 100$ .
- Baseline results are defined as the last assessment prior to first dose of study drug, for subjects randomized to once daily enzalutamide. For subjects randomized to active surveillance, baseline is defined as the last assessment prior to or on the date of randomization.
- Treatment Emergent Adverse Events (TEAEs) are any AEs occurring on or after date of first study drug dose date (or randomization for AS) until 30 days post-treatment end date (or 1-year plus 30 days for AS).
- Treatment Phase is defined as date of first study drug dose (or randomization for AS) until either 30 days post treatment end date or (if earlier) study discontinuation date.
- 1-Year Follow-Up Phase is defined as 31 days post treatment end date until either completing 1-Year Follow-Up or (if earlier) study discontinuation date.
- Continued Follow-Up Phase is defined as the day after completing 1-Year Follow-Up phase until study discontinuation date.

Study Day is defined using the following step-wise function:

- If date of interest is on or following randomization, Study Day = Date of Interest – Randomization Date + 1;
- Else, Study Day = Date of Interest – Randomization Date.

Change from baseline is the difference between the result on a post baseline visit and baseline assessment.

Rise in serum PSA is defined as  $PSA \geq 25\% \text{ of baseline or } \geq 25\% \text{ above nadir or } \text{absolute increase} > 2\text{ng/mL}$ .

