### 7.5.1 Adverse Events

All AEs will be collected and the severity of the AEs will be evaluated by the investigator based on Version 4.03 of the NCI-CTCAE criteria, updating to the latest version per sponsor decision. All AEs will be coded using the Version 23.0 of the Medical Dictionary for Regulatory Activities (MedDRA) to preferred term, high-level term and system organ class, up versioning every two years per sponsor decision.

Adverse events occurring before randomization will be recorded as medical history events. To maintain naming consistency with subjects on Active Surveillance (AS), Treatment-Emergent Adverse Events (TEAEs) for subjects on Enzalutamide will be reported as Adverse Events (AEs).

An overall summary table will be included that has the following information by treatment group and overall by analysis phase (Treatment, 1-Year Follow-Up and Continued Follow-Up):

- Number and percentage of subjects with AEs
- Number and percentage of subjects with causally drug-related AEs
- Number and percentage of subjects with serious AEs
- Number and percentage of subjects with serious drug-related AEs
- Number and percentage of subjects with AEs leading to permanent discontinuation of study drug,
- Number and percentage of subjects with drug-related AEs leading to permanent discontinuation of study drug
- Number of deaths.

Furthermore, the number of events and number (%) of subjects with AEs, drug-related AEs, serious AEs, drug-related serious AEs, AEs leading to permanent discontinuation of study drug, drug-related AEs leading to permanent discontinuation of study drug, and common AEs occurring in at least 3.5% of any treatment group will be summarized by MedDRA system organ class and preferred term by treatment group and overall. Additional summary tables will be provided for AEs by relationship to study treatment and by CTCAE maximum severity grade. For subjects with missing relationship, the most conservative (related) will be assumed for table summaries.

If a subject reports the same event multiple times, the event will only be displayed once in the summary tables at the highest grade and relationship to study drug.

Version 4.03 of the NCI-CTCAE criteria, updating to the latest version per sponsor decision, will be used to classify laboratory values by toxicity grade.

Listings of AEs, SAEs, Deaths and AEs leading to study drug discontinuation will be displayed by treatment group and site.

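### The only CTCAE-graded laboratory shift table takes the worst grade over all post-baseline visits, so on-drug and off-drug grades cannot be told apart

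*SAP*

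**What the plan says.** Four parts of the SAP bear on this.

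- **Window of the graded table.** Section 7.5.2 has the CTCAE shift tables "report the baseline NCI-CTCAE grade vs. the worst grade recorded at any post-baseline visit", with no limit by phase or time since last dose. The other laboratory shift tables in that section are by visit, but classify values only as low, normal or high.
- **Drug period and sampling.** Section 3.2 gives enzalutamide or AS "during the one year study treatment period", and adds that "Subjects will be followed up every 3 months for these 2 years". Section 7.5.2 states: "Clinical laboratory assessments will be done at every scheduled visit, as well as at any unscheduled visits". Table 2 marks clinical laboratory tests at months 3, 6, 9, 12, 15, 18, 21 and 24, and again after month 24. Its first footnote says: "Subjects will be followed every 6 months until the last subject (study-wide) has completed the 24m Visit".
- **Phases.** Section 6.4 sets three phases. "Treatment Phase is defined as date of first study drug dose (or randomization for AS"), and it ends 30 days after treatment end or at study discontinuation if earlier. For AS, the same section closes the treatment-emergent AE window at one year plus 30 days.
- **Use of the phases.** Section 7.5.1 presents the overall AE summary "by treatment group and overall by analysis phase (Treatment, 1-Year Follow-Up and Continued Follow-Up"). Section 7.5.2 does not use the phases.

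**The concern.** The question a graded laboratory shift table should answer is how often a subject's grade worsened while exposed to the drug, compared with AS over the same time. A worst grade over all visits answers another question: how often it worsened at any time in two years or more, half of them without drug in the enzalutamide arm. Follow-up values obtained after prostatectomy, radiation or systemic therapy also count, because nothing in 7.5.2 excludes them.

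No other planned table fills the gap. The by-visit shifts show on-drug visits, but not CTCAE grade and not a worst value per subject. The graded table also cannot be read beside the phase-split AE overview. What is at stake is the interpretability of one safety table; no efficacy conclusion is touched.

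**Working it through.** The SAP states no figure for this table, so there is none to reproduce.

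**1. Visits on and off drug (Table 2, section 3.2).** On drug: months 3, 6, 9 and 12, that is 4 visits. After the drug year: months 15, 18, 21 and 24, that is 4 visits. Month 15 is day 455. One year plus 30 days is about day 365 + 30 = 395, so month 15 lies outside the Treatment Phase for a subject treated as planned. For a 24-month completer the off-drug share is 4/8 = 50%.

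**2. Visits after month 24.** Section 4 assumes subjects "accrued over one year, a study duration of 3 years, loss-to follow-up of 16"%. With one-year accrual, at most months 30 and 36 are added: 5/9 = 56% or 6/10 = 60% off drug. Whether laboratory tests are done then is unclear. Table 2 marks them; section 3.2 names only PSA and digital rectal examination for those visits; section 7.5.2.1 runs liver tests to month 24. The 4-of-8 count holds either way.

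**3. Dropout.** Let S(t) be the proportion still in study at month t, with a constant loss rate. Each off-drug visit is 12 months after an on-drug one, so the off-drug share through month 24 is S(12)/[1 + S(12)].

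- 16% read as loss over 3 years: S(12) = 0.84^(1/3) = 0.9435, share = 0.9435/1.9435 = 48.5%.
- 16% read as loss per year: S(12) = 0.84, share = 0.84/1.84 = 45.7%.

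If half of the subjects also have a month-30 laboratory visit, the share is about 48–51%.

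**4. Effect on the contrast.** Assume independent visits, a per-visit risk q0 of a worsened grade off drug and in AS, a risk q1 on drug, and m off-drug visits.

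- AS: 1 − (1 − q0)^(4+m)
- Enzalutamide: 1 − (1 − q1)^4 × (1 − q0)^m
- Difference: (1 − q0)^m × [(1 − q0)^4 − (1 − q1)^4], so the difference shrinks only by the factor (1 − q0)^m.

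For q0 = 2% and q1 = 5%:

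- m = 0: AS 1 − 0.98^4 = 7.8%; enzalutamide 1 − 0.95^4 = 18.5%; ratio 2.39; difference 10.8 points.
- m = 4: AS 1 − 0.98^8 = 14.9%; enzalutamide 1 − 0.8145 × 0.9224 = 24.9%; ratio 1.67; difference 9.9 points.
- m = 6: ratio 1.52; difference 9.6 points.

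Other assumed pairs, 4 visits against 8 visits:

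| q0, q1 | Ratio, 4 visits | Ratio, 8 visits | Difference (points), 4 visits | Difference (points), 8 visits |
|---|---|---|---|---|
| 0.2%, 1% | 4.94 | 2.96 | 3.1 | 3.1 |
| 0.5%, 2% | 3.91 | 2.44 | 5.8 | 5.7 |
| 1%, 3% | 2.91 | 1.94 | 7.5 | 7.2 |
| 2%, 4% | 1.94 | 1.45 | 7.3 | 6.7 |
| 2%, 6% | 2.82 | 1.88 | 14.2 | 13.1 |
| 5%, 10% | 1.85 | 1.38 | 15.8 | 12.9 |

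The ratio falls in every row. The difference falls by at most 1.1 points in the first five rows, and by 2.9 points in the last, where background abnormality is most frequent.

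**The case against.** A reader might infer that the table dilutes or hides on-drug laboratory toxicity. The SAP does not support that: adding visits to a maximum can leave a subject's worst grade unchanged or raise it, never lower it. Every on-drug grade remains, and the absolute difference between arms changes little unless background abnormality is common. That part of the objection stands in full.

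A reader might also infer that at least half of all graded visits in the trial are off drug. That is exact only for the schedule of a 24-month completer; dropout takes the share slightly below half through month 24. Subjects who stop drug early have a larger off-drug share.

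The per-visit risks are assumed. Independence is too: repeated values in one subject are usually correlated, so later visits would add fewer new worst grades than shown.

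Nor is this a contradiction with the AE section. Section 7.5.1 states the phase split for the overall AE summary, and states none for the tables by system organ class or maximum grade. An all-visit worst grade is a legitimate summary that also catches late abnormalities. The by-visit shifts, the summaries of actual values and change, and the hepatic criteria of 7.5.2.1 give partial cover, and the separate table specifications may add detail.

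What survives is narrower: as written, the SAP plans no table giving the worst on-drug CTCAE grade by arm.

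**Conclusion.** The point holds as a modest improvement to safety reporting. The window in 7.5.2 is a stated rule, and it mixes grades from the drug year with grades from at least as many later scheduled visits in a 24-month completer. The consequences are higher percentages in both arms, worst grades that cannot be attributed to drug exposure, and a ratio nearer to 1. The direction of the ratio effect follows from pooling equal background risk into both arms; its size rests on assumed risks and independent visits.

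Later prostate cancer therapy could enter the arms unequally, since section 4 assumes progression hazards of 0.2310 for control and 0.1189 for treatment. The SAP gives no basis for sizing that effect on laboratory grades, and none is claimed here.

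**What to change.** In section 7.5.2, define the main graded shift table as baseline against worst grade over one fixed window that is the same in both arms: from first dose (randomization for AS) to one year plus 30 days. Keep the all-visit table as a supplement.

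A further version by the section 6.4 phases may be added to sit beside the AE overview. It should carry a note that the Treatment Phase ends 30 days after each subject's last treatment, so it is shorter for subjects who stop drug early and is not the same window as the fixed one. That is why the fixed window is preferable for the comparison between arms.

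The cost is one or two extra tables from data already collected. Visits, sample size and other analyses do not change.
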